8.4. Unscheduled Visits

If a study participant develops eye signs or symptoms [decreased visual acuity, redness (above baseline), pain] after completion of the study drug administration (i.e. Day 5 and onward) they should be scheduled for a full ophthalmic examination after discharge or at the end of Day 28+/-7 days. The study team will schedule this examination and the study will pay for this visit.

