6.5. Premature Discontinuation of Investigational Agent

Participants may be discontinued from the study at any time for the following reasons:

- a. Suspected allergy or anaphylaxis. The study drug infusion must be discontinued, and the participant must be discontinued from further study treatment if the participant develops signs and symptoms of anaphylaxis or hypersensitivity fulfilling the following criteria (Sampson et al. 2006):

Acute onset of an illness (minutes to several hours) with involvement of the skin, mucosal tissue, or both (e.g., generalized hives, pruritus or flushing, swollen lips-tongue-uvula) and at least one of the following:

- i. Respiratory compromise (e.g., dyspnea, wheeze-bronchospasm, stridor, reduced peak expiratory flow (PEF), hypoxemia); or
- ii. Reduced BP or associated symptoms of end-organ dysfunction (e.g., hypotonia [collapse], syncope, incontinence)

Note: Collect a blood for serum tryptase measurement as soon as possible (within 60 minutes) after emergency treatment for suspected anaphylaxis. Collect another blood sample for tryptase levels between 60-120 minutes (but no later than 4 hours) after emergency treatment. If the first sample cannot be obtained within the first 60 minutes the second sample should still be obtained. In addition a baseline serum tryptase should be obtained 24 hours or more after the onset of symptoms. An elevated serum tryptase will support the diagnosis of anaphylaxis (NICE 2020). Respiratory compromise, reduced BP, or symptoms of end-organ dysfunction determined by the PI to be related to the underlying SARS-CoV-2 infection should not be considered as one of the clinical criteria for a severe allergic reaction listed above. The Site Principal Investigator should contact the VCC Medical Monitor to determine whether to discontinue study treatment for a given participant not meeting these criteria but for whom there is a clinical suspicion of a significant allergic reaction or possible anaphylaxis.

- b. Eye symptoms. If a participant develops eye symptoms such as decreased visual acuity, significant redness (above baseline), pain, or light sensitivity, they should be discontinued from study drug and scheduled for a full ophthalmic examination with slit-lamp examination as soon as feasible.

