8.3.3. Daily Evaluations While Hospitalized

- Record vital signs (blood pressure, weight, respiratory rate, heart rate and temperature).
- Assessment for adverse events (medical record, bedside nurse, and patient if possible).
- Record concomitant medications
- Determine and record Eight-Point Ordinal Scale performed twice daily as close as possible to 8:00 a.m. and 8:00 p.m. (Appendix C).
- Record oxygenation (SpO₂ and/or PaO₂) and supplemental oxygen delivery (nasal cannula flow, high-flow nasal cannula – FiO₂ and flow, non-invasive ventilation (CPAP level, FiO₂), invasive ventilation (PEEP, FiO₂) daily).
- Document presence or absence of eye symptoms, including decreased visual acuity, conjunctival redness, light sensitivity or pain in the eyes. If eye symptoms are present, discontinue dosing if still ongoing and schedule an eye examination as soon as feasible. If eye symptoms occur after dosing has been completed, schedule an eye examination as soon as feasible, but the participant may continue in the study and have all scheduled evaluations.
- Record date and time of participant death. Complete serious adverse event reporting requirements (see Section 12.4). Document whether death occurred after withdrawal of life support and/or comfort measures.
- Collect blood and process serum for tryptase between 60-120 minutes (but no later than 4 hours) after emergency treatment if participant has suspected allergic reaction/anaphylaxis post infusion (see section 6.5) .
- Unscheduled sampling of anti-drug antibodies should be performed if participant has a suspected immunologically related adverse event.
- Record complete blood count (hematocrit/hemoglobin, platelet count, white blood cell count with differential), PT/INR/PTT, Complete metabolic panel (serum sodium, bicarbonate, potassium, blood urea nitrogen, creatinine, AST, ALT, alkaline phosphatase, total bilirubin), ferritin, CRP, LDH, D-dimer , if collected as part of clinical care.

Record value obtained closest to 8:00 AM on study day.

- Document whether medical care is provided under conventional, contingency, or crisis standards of care.

8.3.4. Study Day 2

- Conduct all study evaluations in Section 8.3.3, Daily Evaluations While Hospitalized.
- Determine and record Eight-Point Ordinal Scale performed twice daily as close as possible to 8:00 a.m. and 8:00 p.m. (Appendix C)

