- Record variables for Sequential Organ Failure Assessment score (SOFA; Appendix A).
- Draw the following labs if not collected as part of clinical care (values closest to 8:00 am on study day):
Complete blood count (hematocrit/hemoglobin, platelet count, white blood cell count with differential), PT/INR/PTT, Complete metabolic panel (serum sodium, bicarbonate, potassium, blood urea nitrogen, creatinine, AST, ALT, alkaline phosphatase, total bilirubin), ferritin, CRP, LDH, D-dimer. If not still hospitalized record the most recent lab values.
- Collect blood for study labs, if still hospitalized
 - Process and freeze (-80°C) plasma for prognostic biomarkers.
 - Process and freeze (-80°C) serum for PK. (40 participants)
- Collect nasal swab for viral detection.

8.3.10. Study Day 21 (if hospitalized) Conduct all study evaluations in Section 8.3.3, Daily Evaluations While Hospitalized.

- Determine and record Eight-Point Ordinal Scale performed twice daily as close as possible to 8:00 a.m and 8:00 p.m. (Appendix C).
- Record variables for Sequential Organ Failure Assessment score (SOFA; Appendix A).
- Draw the following labs if not collected as part of clinical care (values closest to 8:00 am on study day): Complete blood count (hematocrit/hemoglobin, platelet count, white blood cell count with differential), PT/INR/PTT, Complete metabolic panel (serum sodium, bicarbonate, potassium, blood urea nitrogen, creatinine, AST, ALT, alkaline phosphatase, total bilirubin), ferritin, CRP, LDH, D-dimer. If not still hospitalized record the most recent lab values.
- Collect blood for study labs, if still hospitalized
 - Process and freeze (-80°C) plasma for prognostic biomarkers

8.3.11. Study Day 28

It is preferred that this visit is in person to obtain safety laboratory tests as well as clinical outcome data. However, infection control or other restrictions may limit the ability of the participant to return to the clinic. In this case, the visit may be conducted by phone or virtually, and only clinical data will be obtained. All participants will undergo an ocular examination. This examination will be scheduled as a separate in-person visit, usually in the ophthalmology clinic. This visit should be completed at 28 +/- 1 day to obtain the Eight-Point Ordinal Scale and survival. Chest x-ray and labs should be obtained at this visit or as soon as possible after the visit.

- Record adverse events.

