11.1. Participant Completion

The study will be complete for each participant at the end of the Day 60 visit.

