- b. Eye symptoms or signs. If a participant develops eye symptoms such as decreased visual acuity, significant redness (above baseline), pain, or light sensitivity, they should be discontinued from study drug and scheduled for a full ophthalmic examination with slit-lamp examination as soon as feasible.
- c. New infections. If a participant develops a proven or suspected new infection during the 4 days of study drug treatment, the study drug should be discontinued, and the patient should be treated by participant's primary physicians as clinically appropriate.
- d. Other safety concerns. The Site Principal Investigator is authorized to discontinue the study drug at any time if it is in the best interest of the safety of the participant. Treatment may also be discontinued at any time at the request of the study participant.

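### For eye symptoms that begin after dosing, section 8.4 sets no prompt timing for the full examination and omits light sensitivity, and nothing links it to the faster rules in 8.3.3, 6.5 b and 11.2

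*Combined protocol and SAP*

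**What the plan says.** Four provisions in the protocol link eye symptoms to an eye examination.

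- **Section 8.4 (Unscheduled Visits)** applies when a participant "develops eye signs or symptoms [decreased visual acuity, redness (above baseline), pain] after completion of the study drug administration", which it equates with Day 5 onward. The instruction is that "they should be scheduled for a full ophthalmic examination after discharge or at the end of Day 28+/-7 days". The study team books this visit and the study pays for it.
- **Section 8.3.3 (Daily Evaluations While Hospitalized)** has staff check every day: "Document presence or absence of eye symptoms, including decreased visual acuity, conjunctival redness, light sensitivity or pain in the eyes". For onset after the last dose it adds: "If eye symptoms occur after dosing has been completed, schedule an eye examination as soon as feasible".
- **Section 6.5 b** says of participants who develop eye symptoms that "they should be discontinued from study drug and scheduled for a full ophthalmic examination with slit-lamp examination as soon as feasible". Its examples include light sensitivity.
- **Section 11.2, item 5 b** repeats that rule, with the participant "scheduled for a full ophthalmic examination with slit-lamp examination as soon as feasible".

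Separately, every participant is to have a routine full ocular examination once stable and out of quarantine, typically between Day 28 and Day 60 (8.3.11, 8.3.12, Table 3 note 3, 13.3). Of this one, 8.3.11 says: "This examination will be scheduled as a separate in-person visit, usually in the ophthalmology clinic". Eye abnormalities, including light sensitivity and photophobia, are adverse events of special interest (12.4.3.1). On duration, 11.1 says: "The study will be complete for each participant at the end of the Day 60 visit".

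**The concern.** An inpatient with eye pain on Day 6 falls under both 8.3.3 and 8.4. One asks for an examination as soon as feasible; the other lets the full examination wait. Neither refers to the other. A discharged participant falls outside 8.3.3, and 8.4 is the text written for the period after dosing, so a coordinator would naturally follow it. It neither requires nor forbids a prompt examination. A discharged participant with light sensitivity alone has a listed event of special interest but does not meet 8.4's trigger.

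What is at stake is the care of a symptomatic participant and the quality of the ocular safety information, not the efficacy analysis. The sponsor's own standard in 6.5 b and 11.2 is a prompt slit-lamp examination for these symptoms, and no reason is given for a looser one from Day 5. Section 5.1 reports vitreous cells in dosed primates that cleared over the following 28 days. If something similar and transient occurred in humans, a late examination could miss it. That is an inference; the same section calls the primate finding minor.

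**Working it through.** There is no figure in the plan to reproduce. The check is a comparison of texts plus date arithmetic.

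**Provisions side by side**

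| Section | Covers | Examination | Timing | Light sensitivity listed |
|---|---|---|---|---|
| 6.5 b | Eye symptoms, no onset limit; first action is to stop study drug | Full, with slit lamp | As soon as feasible | Yes |
| 11.2, item 5 b | As 6.5 b | Full, with slit lamp | As soon as feasible | Yes |
| 8.3.3, post-dosing sentence | Inpatients | Eye examination, type not stated | As soon as feasible | Yes |
| 8.4 | Any participant, Day 5 onward | Full ophthalmic | After discharge, or the Day 28 window | No |
| 8.6 telephone visits | Discharged participants | None; ordinal scale and adverse events recorded | Not applicable | Not applicable |
| 12.4.3.1 | All | None; a collection and reporting rule | Not applicable | Yes |
| 8.3.11, 8.3.12, 13.3 | All, no symptom needed | Full routine examination | Once stable, typically Day 28 to Day 60 | Not applicable |

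Three things follow.

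1. *Timing.* 8.4 is the only symptom-triggered provision in the table that does not ask for an examination as soon as feasible.
2. *Trigger.* 8.4 gives a bracketed list of three items. The lists in 6.5 b, 11.2 and 8.3.3 are open-ended and name light sensitivity as well.
3. *Reach of 6.5 b and 11.2.* Their action, stopping study drug, has no meaning once dosing is over. Yet they carry no time limit, whereas the new-infection item that follows in each list is expressly confined to the four treatment days. Either reading is arguable.

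**Delay under the Day 28 option.** I take Day 28 +/- 7 to mean a window:

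- Opens: 28 - 7 = Day 21. Closes: 28 + 7 = Day 35.
- Onset Day 5: 21 - 5 = 16 days to 35 - 5 = 30 days.
- Onset Day 14: 21 - 14 = 7 days to 35 - 14 = 21 days.

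**Delay under the after-discharge option.** No latest date is given, so there is no upper bound to calculate. There is no lower bound either: a participant already at home can be examined at once. The sample size section (13.11) assumes a median of 6 days to recovery on placebo. Recovery includes leaving hospital, but also category 3 (still in hospital), so this is only a rough sign that the option opens early for many participants.

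**Onset after Day 35.** The Day 28 window has closed, but participation runs to Day 60. The after-discharge option remains, still without a time limit.

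**The case against.** The best defence is that the texts do not collide. 8.3.3 asks for an eye examination and 8.4 for a full ophthalmic one. A prompt check followed by a full examination satisfies both, and the conditions on the routine examination (stable, out of quarantine, able to comply) suggest why the full one might wait. This stands: a reader might infer two instructions that cannot both be obeyed, and the documents do not support that. What remains is that no text states the two-step scheme.

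A reader might also infer that after discharge 8.4 is the sole symptom-triggered rule. That goes too far, because 6.5 b and 11.2 have no stated end date and can be read literally as still applying. If they do apply, 8.4 is out of step with them, and the same amendment is needed.

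Nor should the 16 to 30 days be taken as the expected delay. They describe one of two alternatives. Likewise, the closing of the window on Day 35 does not leave later onsets without provision, since a discharged participant can be seen immediately.

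Finally, there are real safeguards: daily inpatient eye checks (8.3.3), adverse events taken at telephone visits (8.6) and followed to resolution or the end of participation (12.4.3), monthly review of events of special interest (12.5.1.1), weekly line listings (12.7.1, 12.7.2), and a slit-lamp examination for everyone (13.3). These make serious harm from the wording less likely. They do not set a time for examining a symptomatic eye.

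**Conclusion.** The point holds as a weakness of wording with a practical safety consequence. As written, 8.4 permits avoidable delay before a full examination for reduced acuity, redness or pain that begins after dosing: up to 30 days for a Day 5 onset under the Day 28 option, and no stated limit under the other. It also leaves out light sensitivity, and its relation to 8.3.3, 6.5 b and 11.2 is unstated.

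The delays assume that Day 28 +/- 7 means Day 21 to Day 35 and that a site uses that option. The documents give no rate of eye symptoms in this population, so the number affected cannot be estimated. It is probably small: 5.1 reports no eye findings in 63 treated people who had eye examinations. A reader might infer bias between arms or undercounted events of special interest. The documents do not support either, because event collection does not depend on 8.4. The primary endpoint and power are untouched. This is a low-cost improvement, at the lowest level of importance.

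**What to change.** Amend 8.4 to say that decreased visual acuity, redness above baseline, pain or light sensitivity beginning after dosing, in hospital or after discharge and up to Day 60, leads to a full ophthalmic examination with slit lamp as soon as feasible, allowing for isolation and clinical stability. Add cross-references to 8.3.3 and 6.5 b, and state that this examination is separate from the routine one between Day 28 and Day 60.

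This carries the slit-lamp standard of 6.5 b and 11.2 explicitly into the post-dosing period, and asks for more than the unspecified eye examination in 8.3.3. The cost is a few sentences. Some examinations that are already funded will come earlier, possibly under isolation precautions, and a few may be added for isolated light sensitivity. The change does not improve detection of late symptoms: 8.3.12 lists only serious adverse events for recording at Day 60, and the wording proposed here leaves that as it is.

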8.5. Visit Windows

Study monitoring should take place daily through Day 28 or as long as the participant is hospitalized. For participants who are discharged prior to day 28, the Day 28 visit should be completed remotely within +/- 1-day window if the participant is unable to return to the clinic. Likewise, if the participant has been discharged, the Day 14 and 21 visits should be completed remotely if the participant is unable to return to the clinic. The Day 60 visit should occur in person if possible, within a +/- 3-day window. If unable to return to the clinic this visit can occur remotely.

8.6. Telephone visits

If a study participant has been discharged prior to one of the scheduled Study Day visits, then that study visit should be conducted by telephone to ascertain the participant's clinical status. Determine and record Eight-Point Ordinal Scale and record adverse events.

8.7. Reimbursement for Study Visits

Study participants will not be reimbursed for time during hospital monitoring. Study participants who are outpatients will be reimbursed for their time for telephone interviews and in-person outpatient visits.

9. Mechanistic Assays

Mechanistic assays will be performed on stored blood samples collected during the study. These assays include serum measurements of soluble CD14 (sCD14), inflammatory biomarkers (CRP, ferritin, LDH), and cytokines (TNF α , IL-1 β , IL-6, IL-8, IL-10, GM-CSF and others). We expect that sCD14 will rise in serum, reflecting complexing with the IC14 anti-CD14 monoclonal antibody. We expect that inflammatory biomarkers and cytokines will fall in participants treated with the IC14 monoclonal antibody.

10. Biospecimen Storage

Aliquots of serum and plasma will be stored frozen in the University of Washington Central Research Laboratory and analyzed in batches after the final participant has completed the study. Left over aliquots of serum and plasma will be stored frozen (-80C) in a biorepository of participant samples at a location approved by DAIT/NIAID. The biorepository samples will be coded and will be permanently unlinked from the patient's clinical information collected during the study and the hospitalization for COVID-19 illness.

11. Criteria for Participant and Study Completion and Premature Study Termination

11.1. Participant Completion

The study will be complete for each participant at the end of the Day 60 visit.

11.2. Participant Stopping Rules and Withdrawal Criteria

Participants may be prematurely terminated from the study for the following reasons:

1. The participant elects to withdraw consent from all future study activities, including follow-up.

2. The participant is “lost to follow-up” (i.e., no further follow-up is possible because attempts to reestablish contact with the participant have failed).
3. The participant dies.
4. The Investigator no longer believes participation is in the best interest of the participant.
5. Individual safety stopping rules:
 - a. Suspected allergy or anaphylaxis. The study drug infusion must be discontinued, and the participant must be discontinued from further study treatment if the participant develops signs and symptoms of anaphylaxis or hypersensitivity fulfilling the following criteria (Sampson et al. 2006):

Acute onset of an illness (minutes to several hours) with involvement of the skin, mucosal tissue, or both (e.g., generalized hives, pruritus or flushing, swollen lips-tongue-uvula) and at least one of the following:

- i. Respiratory compromise (e.g., dyspnea, wheeze-bronchospasm, stridor, reduced peak expiratory flow (PEF), hypoxemia); or
- ii. Reduced BP or associated symptoms of end-organ dysfunction (e.g., hypotonia [collapse], syncope, incontinence)

Note: Collect a blood sample for serum tryptase measurement as soon as possible (within 60 minutes) after emergency treatment for suspected anaphylaxis. Collect another blood sample for tryptase levels between 60-120 minutes (but no later than 4 hours) after emergency treatment. If the first sample cannot be obtained within the first 60 minutes the second sample should still be obtained. In addition a baseline serum tryptase should be obtained 24 hours or more after the onset of symptoms. An elevated serum tryptase will support the diagnosis of anaphylaxis (NICE 2020). Respiratory compromise, reduced BP, or symptoms of end-organ dysfunction determined by the PI to be related to the underlying SARS-CoV-2 infection should not be considered as one of the clinical criteria for a severe allergic reaction listed above. The Site Principal Investigator should contact the study monitor to determine whether to discontinue study treatment for a given participant not meeting these criteria but for whom there is a clinical suspicion of a significant allergic reaction or possible anaphylaxis.

- b. Eye symptoms or signs. If a participant develops eye symptoms such as decreased visual acuity, significant redness (above baseline), pain, or light sensitivity, they should be discontinued from study drug and scheduled for a full ophthalmic examination with slit-lamp examination as soon as feasible.
- c. New infections. If a participant develops a proven or suspected new infection during the 4 days of study drug treatment, the study drug should be discontinued, and the patient should be treated by participant's primary physicians as clinically appropriate.
- d. Other safety concerns. The Site Principal Investigator is authorized to discontinue the study drug at any time if it is in the best interest of the safety of the participant. Treatment may also be discontinued at any time at the request of the study participant.

11.3. Participant Replacement

Randomized participants will not be replaced for any reason.

11.4. Follow-up after Early Study Withdrawal

If a participant receives one or more doses of the study drug and withdraws from the study for any reason, the study team should ask the participant if they would be willing to be followed by the study team for the duration of the study,

i.e. through Day 60 in order to determine the participant's clinical status and to assess for any adverse events that might be attributable to the study drug.

